2. OBJECTIVES AND ENDPOINTS

This study will estimate effectiveness of pirfenidone in patients with idiopathic pulmonary fibrosis. Specific objectives and corresponding endpoints for the study are outlined in [Table 1](#) below.

Table 1 Objectives and Corresponding Endpoints

Objectives	Corresponding Endpoints
Primary Efficacy Objective:	Primary Efficacy Endpoint:
To estimate the treatment effect of pirfenidone 2403 mg/d on lung function	Change from Baseline to Week 26 in absolute mL forced vital capacity (FVC) and % FVC.
Secondary Efficacy Objective:	Secondary Efficacy Endpoints:
To estimate the effectiveness of pirfenidone on IPF patients' functional capability and quality of life	
 • Change from baseline to Week 26 in 6-minute walk test (6MWT) distance • Change from baseline to Week 26 in patients' quality of life as measured with European Quality of Life 5-Dimension Questionnaire (EQ-5D)
Exploratory Efficacy Objective:	Exploratory Efficacy Endpoints:
To estimate the effectiveness of pirfenidone on the frequency and number of acute exacerbations of IPF and on features of HRCT	
 • Frequency and number of IPF exacerbations • CT scan evaluation (semiquantitative assessment "HRCT fibrosis score". The high-resolution computed tomography (HRCT) findings will be evaluated using HRCT scoring system. Interstitial lung disease (ILD) radiologist will make assessment of 4 main findings in three zones of each lung. The six zone scores will be averaged to determine the total score for each patient at baseline and at Weeks 26 and 52))
Safety Objective:	Safety Endpoints
To evaluate the safety of pirfenidone	
 • Treatment-emergent adverse events (AEs) • Treatment-emergent serious adverse events (SAEs) • Change from baseline in clinical laboratory parameters and electrocardiogram (ECG) parameters

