Evaluation of the number of exacerbations is a clinically significant outcome but can only serve as an exploratory additional outcome, due to the low frequency of such events, and low number of patients in the trial.

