4.4.1 Permitted Therapy

Corticosteroids may be used permanently at the discretion of the investigator as a part of routine management of IPF (at a maximum daily dose of 15 mg of prednisolone or equivalents). Corticosteroids may also be used without dose restriction for a period of up to 21 days in patients experiencing an episode of acute IPF exacerbation. The study drug should be continued during exacerbations, if possible. If study treatment interruption or discontinuation is considered, it must be immediately reported by telephone to Sponsor's Medical Monitor or designee.

An acute IPF exacerbation is defined in updated publication (Collard HR et al., 2016).

The diagnostic criteria:

- Previous or concurrent diagnosis of IPF;
- Acute worsening or development of dyspnea typically <1 mo duration;
- Computed tomography with new bilateral ground-glass opacity and/or consolidation superimposed on a background pattern consistent with usual interstitial pneumonia pattern;
- Deterioration not fully explained by cardiac failure or fluid overload.

Patients who use oral contraceptives, hormone-replacement therapy, or other maintenance therapy should continue their use.

Pirfenidone—F. Hoffmann-La Roche Ltd

93/Protocol ML39355, Version 2 dated 09-Jun-2018

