5.2.1 Adverse Events

According to the ICH guideline for Good Clinical Practice, an adverse event is any untoward medical occurrence in a clinical investigation subject administered a pharmaceutical product, regardless of causal attribution. An adverse event can therefore be any of the following:

Pirfenidone—F. Hoffmann-La Roche Ltd

- Any unfavorable and unintended sign (including an abnormal laboratory finding), symptom, or disease temporally associated with the use of a medicinal product, whether or not considered related to the medicinal product
- Any new disease or exacerbation of an existing disease (a worsening in the character, frequency, or severity of a known condition), except *exacerbation or worsening of IPF*. *Worsening of IPF (i.e. IPF progression) is considered as an AE only in case of fatal outcome attributed to this progression (as described in [Section 5.3.5.7](#))*.
- Recurrence of an intermittent medical condition (e.g., headache) not present at baseline
- Any deterioration in a laboratory value or other clinical test (e.g., ECG, X-ray) that is associated with symptoms or leads to a change in study treatment or concomitant treatment or discontinuation from study drug
- Adverse events that are related to a protocol-mandated intervention, including those that occur prior to assignment of study treatment (e.g., screening invasive procedures such as biopsies)
- Lack of efficacy is not considered as AE

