3.1.3. Exploratory Efficacy Objective

To estimate the effectiveness of pirfenidone on the frequency and number of acute exacerbations of IPF and on features of HRCT.

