8.3. Exploratory Efficacy Analyses

eCRF form: “HRCT SCAN”, “ADVERSE EVENTS”.

HRCT fibrosis score

The HRCT findings will be evaluated using HRCT scoring system. One ILD radiologist will make assessments of 4 main findings in three zones of each lung. The six zone scores will be averaged to determine the total score for each patient. Score will be recorded at the initial diagnosis and after six and 12 months in a similar manner for further comparison. The mean \pm SD of HRCT fibrosis score like continuous variable will be determined obligatory at baseline, 6 months and optional at 12 months.

The values of HRCT fibrosis score at baseline, at Week 26 and Week 52 (optional) will be summarized in table with standard descriptive statistics for continuous variables and 95% CI for the mean.

Additionally, the absolute change of HRCT fibrosis score from baseline at Week 26 and Week 52 (optional) will be summarized in table with standard descriptive statistics for continuous variables and 95% CI for the mean.

The paired t-test will be performed to evaluate the changes in the variable from the baseline to Week 26 and Week 52 (optional), respectively. The type I error rate will be set to 5%.

Lung opacity (ground-glass attenuation)

The sign ‘lung opacity’ will be qualified separately using methodology described above for other signs, and its change over time will be assessed outside the framework of a total summed index of fibrosis (HRCT fibrosis score). Lung opacity should be graded as reticular abnormality to calculate the score for each zone, i.e. the percentage (%) area of opacity in a zone should be multiplied by the score of 2.

The lung opacity score at Baseline, at Week 26 and Week 52 (optional) will be summarized using standard descriptive statistics for continuous variables and 95% CI for the mean.

Additionally, the absolute change of lung opacity score from Baseline at Week 26 and Week 52 (optional) will be summarized in table with standard descriptive statistics for continuous variables and 95% CI for the mean.

**ML39355_STATISTICAL ANALYSIS PLAN_Final 2.0_17 June 2020**Exacerbations

An exacerbation will be defined as an AE with special criteria “Is this an exacerbation of IPF?” = “Yes”, i.e. only in case the exacerbation has led to death of a patient. Rate of exacerbation will be reported in three following tables:

- Exacerbation cases during treatment period (until Week 26).

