16.1. Tables

Patients Disposition

- Table 1.1 Patients disposition (All Enrolled patients)
- Table 1.2 Violation of eligibility criteria (Screening Failures)
- Table 1.3 Analysis populations (Allocated to treatment set)
- Table 1.4 Study visits

Protocol Deviations

- Table 1.5 Protocol deviations / violations (Allocated to treatment set)

Demographic and Anthropometric characteristics

- Table 1.6 Demographic characteristics (TS)
- Table 1.7 Anthropometric characteristics (TS)

Baseline Variables

- Table 1.8 Surgical lung biopsy (TS)
- Table 1.9 HRCT for patient eligibility confirmation (TS)
- Table 1.10 Carbon monoxide diffusing capacity (DLCO) (TS)
- Table 1.11 Pre- and post-bronchodilator spirometry parameters at screening (TS)
- Table 1.12 Serologic tests (TS)
- Table 1.13 GAP assessment (TS)
- Table 1.14 Review transbronchial lung biopsy/BAL (TS)

Medical history

- Table 1.15 Prior medical/surgical conditions/diagnoses (TS)
- Table 1.16 Concurrent medical/surgical conditions/diagnoses (TS)
- Table 1.17 History of idiopathic pulmonary fibrosis (TS)

Prior and concomitant medications

- Table 1.18 Prior medications (TS)
- Table 1.19 Concomitant medications (TS)
- Table 1.20 Concomitant medications during rollover study (TS)

Efficacy Analyses

- Table 2.1 Descriptive statistics for FVC by visit (FAS)
- Table 2.2 Primary efficacy endpoint (FAS)
- Table 2.3 Primary efficacy endpoint: categorical results (FAS)
- Table 2.4 Primary efficacy endpoint by pattern type (CSS)
- Table 2.5 6-Minute Walk Test (FAS)
- Table 2.6 Change in 6MWT distance at Week 26 by category (FAS)
- Table 2.7 Borg scale (FAS)
- Table 2.8 EQ-5D-5L. Descriptive statistics (FAS)
- Table 2.9 Change in EQ-5D-5L. Mobility (FAS)
- Table 2.10 Change in EQ-5D-5L. Self-Care (FAS)
- Table 2.11 Change in EQ-5D-5L. Usual Activities (FAS)
- Table 2.12 Change in EQ-5D-5L. Pain/Discomfort (FAS)
- Table 2.13 Change in EQ-5D-5L. Anxiety/Depression (FAS)
- Table 2.14 EQ-5D-5L. VAS and Index score (FAS)
- Table 2.15 HRCT. HRCT fibrosis score (FAS)
- Table 2.16 HRCT. Lung opacity score (FAS)
- Table 2.17 Exacerbation cases during treatment period (FAS)
- Table 2.18 Exacerbation cases during rollover study (FAS, patients continuing in the rollover study)
- Table 2.19 Exacerbation cases during whole study period (FAS, patients continuing in the rollover study)

Safety Analyses

- Table 3.1 Duration of exposure (TS)
- Table 3.2 Total number of capsules taken (TS)

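### The exploratory endpoint is all acute IPF exacerbations, but the planned tables count only fatal ones, so overall frequency and number are neither planned for analysis nor reliably captured

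*SAP*

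**What the plan says.** Protocol section 2 (Table 1) and SAP 3.2.3 give the exploratory endpoint as "Frequency and number of IPF exacerbations". The objective in SAP 3.1.3 is the effectiveness of pirfenidone "on the frequency and number of acute exacerbations of IPF". Neither mentions fatal outcome.

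Protocol 4.4.1 lists the diagnostic criteria for an acute exacerbation, among them "Acute worsening or development of dyspnea typically <1 mo duration". Death is not a criterion, and the same section provides for treatment to carry on through an episode.

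SAP 8.3 defines an exacerbation as an adverse event for which the form item "Is this an exacerbation of IPF" is answered yes, and then adds "i.e. only in case the exacerbation has led to death of a patient". Protocol 6.4.3 carries the same restriction. Protocol 5.2.1 takes exacerbation and worsening of IPF out of the adverse event definition; worsening "is considered as an AE only in case of fatal outcome attributed to this progression".

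The results go into Tables 2.17 (treatment period), 2.18 (rollover) and 2.19 (whole study, rollover patients only), all on the full analysis set (FAS). Protocol 3.3.5 already restricts the endpoint to exploratory use "due to the low frequency of such events, and low number of patients in the trial".

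**The concern.** The quantity named and the quantity counted are different. A reader of the study report would see an endpoint on exacerbations and tables headed exacerbation cases, and could take a count near zero to mean that few exacerbations occurred on treatment. It would only mean that few patients died of one. The stated objective would go unanswered without the report saying so.

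The choice of analysis set adds to this. Early deaths are the events a fatal-only definition is meant to count, and the FAS is the set most likely to leave them out.

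**Working it through.** The documents state no figure for this endpoint, so the main check sets the definitions side by side.

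| Step | Source | Content |
|---|---|---|
| Objective, endpoint | Protocol 2; SAP 3.1.3, 3.2.3 | all acute exacerbations, frequency and number |
| Clinical definition | Protocol 4.4.1 | criteria without death |
| Recording | Protocol 5.2.1 | non-fatal exacerbation is not an adverse event |
| Data source | SAP 8.3 | adverse event form (the other form listed, HRCT scan, serves the imaging scores) |
| Counting rule | Protocol 6.4.3; SAP 8.3 | fatal only |

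1. An episode that meets the 4.4.1 criteria and is survived falls under the endpoint. Under 5.2.1 it is not an adverse event, so it is not due on the only form the analysis reads.
2. The serious-event route does not recover it. Protocol 5.2.2 defines a serious adverse event as an adverse event meeting further criteria, so a non-fatal exacerbation with hospitalisation is not captured that way either.
3. If a site did enter a non-fatal episode, the counting rule would exclude it from the tables.
4. Tables 2.17 to 2.19 therefore estimate p × f, where p is the risk of an exacerbation and f the share that is fatal. Since f is not collected, p cannot be recovered from them.

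**Illustration of direction only.** Both p (over 26 weeks) and f are assumptions; N = 60 is the planned enrolment. Expected patients with an exacerbation = 60p; expected patients counted = 60pf; chance that the table is empty = (1 − pf)^60.

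| Assumed p | Expected, all (60p) | Expected, counted (f = 25% to 75%) |
|---|---|---|
| 3% | 1.8 | 0.45 to 1.35 |
| 5% | 3.0 | 0.75 to 2.25 |
| 10% | 6.0 | 1.5 to 4.5 |

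At p = 5% the chance of an empty table is (1 − 0.0125)^60 = 47% for f = 25%, 22% for f = 50% and 10% for f = 75%. If all episodes were counted it would be 0.95^60 = 4.6%.

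**Analysis set.** SAP 6.2 admits a treated patient to the FAS only with some post-baseline efficacy measurement. Protocol 4.5.13.5 schedules none at Weeks 2, 4 and 8. The first (EQ-5D, FVC, walk test) are at Week 12 (Protocol 4.5.13.6). A patient who dies of an exacerbation before then would normally be absent from Table 2.17 but present in Listing 24, which covers all enrolled patients. The SAP's own Listing 1 shell shows this pattern: a treated patient, not in the FAS, with death as the reason. As an example, with 60 treated, one such death and everyone else in the FAS, Table 2.17 shows 0/59 while Listing 24 shows one case; on the Treated set it would be 1/60 = 1.7%.

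**Whole-study table.** Rollover patients must have reached Week 26 (SAP 4.1), so almost no fatal case in Table 2.19 can arise before rollover. Under a fatal-only rule it nearly duplicates Table 2.18.

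**The case against.** The strongest reply is that the protocol and the SAP agree. The fatal-only rule stands in both, so it looks deliberate, and the endpoint is exploratory, descriptive and already limited in Protocol 3.3.5. That stands as far as it goes: this is not a conflict between the two documents, and the rule may suit adverse event reporting. It does not explain why the objective, the endpoint and the table titles remain unrestricted.

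Several stronger readings are tempting and should not be adopted.

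- A reader might infer that overall frequency cannot be estimated at all. The eCRF is not among the documents, and the form item does not mention death. Directed history collects hospitalisations and oxygen use, and the medication listing carries indication. These traces are assigned to no exacerbation analysis, and medication collection stops at rollover (Protocol 4.4). What the documents support is that overall frequency is not planned and not reliably captured.
- A reader might size the FAS gap from the Week 12 window, Days 76 to 86 in SAP 7: 75/182 = 41% to 85/182 = 47% of planned treatment days. That is a share of days, not of events. The denominator is not settled either. SAP 9.2 runs the treatment period to 28 days after the last dose for patients who do not roll over, about 182 + 28 = 210 days, which gives 36% to 40%. An unscheduled efficacy measurement could also bring a patient into the FAS.
- A reader might expect Table 2.17 to match Tables 3.10.1 and 3.14. Those cover all adverse events leading to death and all deaths, so they may properly differ. Listing 24 is the like-for-like output.
- A reader might think the rollover restriction on Table 2.19 loses cases. It is openly labelled, and Tables 2.17 and 2.18 between them cover both periods. The table is uninformative as defined, but loses no further case.

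**Conclusion.** The mismatch holds on the current text. Followed as written, the plan describes fatal exacerbations under an endpoint that names all exacerbations. The direction is an undercount; the size is unknown because neither p nor f is given, and the figures above rest wholly on assumed values. The FAS gap is real in principle and foreseen in the Listing 1 shell, but its size is not derivable either.

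The consequence is limited. The endpoint is exploratory, and the fatal-only definition does not affect the primary or secondary endpoints. That does not clear the FAS rule elsewhere: the same rule would drop a death before Week 12 from the primary analysis, which SAP 8.1 intends to impute as FVC = 0. That is a separate issue and is not argued here.

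**What to change.** **Minimum change, no new data.**

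- Retitle the endpoint and Tables 2.17 to 2.19 as *fatal IPF exacerbations*.
- Report them on the Treated set, and base the whole-study table on all treated patients.
- State in SAP 8.3 and in the clinical study report that the overall frequency and number of exacerbations are not estimated.
- Record the change in SAP 14, because Protocol 6.4 puts efficacy on the FAS and SAP 14 now declares full consistency with the protocol.

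The cost is wording in SAP 3 and 8.3 and three table shells, with matching wording in Protocol Table 1 and 6.4.3. SAP 2 allows revision before database soft lock.

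**If data capture can still change.** Record every episode meeting the Protocol 4.4.1 criteria, whatever its outcome, on a separate eCRF page independent of adverse event status. Report patients and episodes, with fatal cases as a subset. This needs a protocol amendment with ethics and regulatory approval (Protocol 9.6), one form and some extra site reporting. The criteria rely on CT and the schedule of activities has no scan at an episode, so capture would depend on CT done in routine care. With the CRF dated July 2019 and the SAP June 2020, part of the capture may have to be retrospective; it should be described as incomplete.

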9.2. Adverse Events

eCRF form: “ADVERSE EVENTS”.

AEs will be reported on a per-patient basis, i.e. counting patients rather than events.

After informed consent has been obtained but prior to initiation of study drug, only serious adverse events caused by a protocol-mandated intervention should be reported.

After initiation of study drug, all adverse events will be reported until 28 days after the last dose of study drug. Additionally, for patients continuing in the rollover part of the study adverse events will be reported until Week 52.

Only treatment emergent AEs will be summarized. In the listings, however, all occurrences of the AEs will be presented. Treatment emergent AEs will be summarized per primary SOC and PT. Severity of treatment emergent AEs will be summarized separately.

Treatment-emergent AE is any reported adverse event that starts after initiation of the study therapy and up to 28 days after the last dose of study therapy.

All registered AEs will be coded using the MedDRA version 22.0 (or further updating) and tabulated in the report with grouping by primary system organ class (SOC) and preferred term (PT).

Number (percentage) of patients and number of AEs will be presented for the Treated Set in the following tables:

- All treatment-emergent AE / SAE;
- Treatment-emergent AE / SAE related to the study drug (“Is the adverse event suspected to be caused by the study drug on the basis of facts, evidence, science-based rationales, and clinical judgment?” = “Yes” including those events where assessment is missing);
- TEAE by maximum severity (Severity, CTCAE v.4.0);
- TEAE related to study drug by maximum severity (Severity, CTCAE v.4.0);
- TEAE leading to the permanent discontinuation of study drug (Action taken with IMP=“Permanently discontinued”);
- TEAE leading to death (AE with Outcome = “Death”) including TEAE related to the study drug;
- TEAE related to the study drug leading to death;
- TEAE of special interest (“Is this an adverse event of special interest?” = “Yes”);
- Non-serious TEAEs that occurred at a frequency of $\geq 5\%$ (if no events occurred at the 5% threshold all non-serious TEAEs will be tabulated).

ML39355_STATISTICAL ANALYSIS PLAN_Final 2.0_17 June 2020

This set of tables will be repeated for the following study periods:

- Treatment period defined as first dose of study drug to last dose of study drug in the treatment period + 28 days or until the first dose in the rollover period (Treated Set).
- Rollover period defined as first dose in the rollover to last dose in the rollover study + 28 days (Treated Set, patient continuing in the rollover study).

Tables of TEAEs by maximum severity will be prepared using the following rules: each SOC / PT category will include only the AEs with the worst severity for each patient. In the Overall category, all AEs of the patient will be presented. Each patient will be counted only once with the worst severity in each SOC and each PT level as well as in the Overall level.

Number of patients who died will be tabulated.

All AEs/SAEs will be listed. Non-treatment emergent adverse events will be identified accordingly in the listing.

9.3. Pregnancies

eCRF form: “URINE PREGNANCY TEST”.

All women of childbearing potential will have a urine pregnancy test at the Screening and on Day 1 before start of treatment. Urine pregnancy tests will be performed repeatedly at specified subsequent visits as scheduled in the Table 1.

The results of these tests and pregnancies episodes will be reported in the listing.

9.4. Clinical Laboratory Evaluations

eCRF form: “HEMATOLOGY”, “SERUM CHEMISTRY”.

Clinical laboratory evaluations as scheduled in the Table 1 include the following parameters:

- hematology (plasma): white blood cells (WBC) count, red blood cells (RBC) count, hemoglobin, hematocrit, platelet count, (relative) differential WBC count (neutrophils, eosinophils, basophils, monocytes, lymphocytes);
- blood chemistry panel (serum or plasma): albumin, alkaline phosphatase (AP), ALT, AST, direct bilirubin, total bilirubin, total protein, cholesterol, creatine kinase (CK), creatinine, triglycerides, gamma-glutamyl transferase (GGT), glucose, lactic dehydrogenase (LDH), calcium, phosphorus, magnesium, potassium, sodium, urea nitrogen, uric acid;

Creatinine clearance should be assessed at the Screening for eligibility confirmation using the following formula by Cockcroft-Gault (Cockcroft DW et al, 1976):

For serum creatinine concentration in mg/dL:

ML39355_STATISTICAL ANALYSIS PLAN_Final 2.0_17 June 2020

$$\text{CrCl (mL/min)} = (140 - \text{age (years)}) \times \text{weight (kg)} \times 1.0 / 72 \times \text{serum creatinine (mg/dL)}$$

For serum creatinine concentration in $\mu\text{mol/L}$:

$$\text{CrCl (mL/min)} = (140 - \text{age (years)}) \times \text{weight (kg)} \times 1.0 / 0.81 \times \text{serum creatinine } (\mu\text{mol/L})$$

For laboratory parameters the following tables will be presented according to section 7:

- descriptive statistics of measured values and changes from baseline (including creatinine clearance);
- shift tables based on comparison with normal range (Lower/Normal/Higher);
- frequency tables for Out of range: No/Yes clinically significant (Yes CS) / Yes non-clinically significant (Yes NCS) for laboratory parameters.

All laboratory data will be listed.

